# PASS INFORMATION

Title	An assessment of a relationship between the exposure to COVID-19 vaccines and risk of thrombotic thrombocytopenia syndrome
Protocol version identifier	1.1
Date of last version of protocol	15/June/2021
EU PAS register number	Study not yet registered
Active substance	AZD12222
Medicinal product	Vaxevria
Product reference	005675
Procedure number	EMEA/H/C/005675/MEA 005
Marketing authorisation holder(s)	
Joint PASS	No
Research question and objectives	To evaluate an association between COVID-19 vaccine exposure and thromboembolic events occurring with thrombocytopenia (thrombotic thrombocytopenia syndrome; TTS).
Country of study	United Kingdom (UK)
Author(s)	

# 2. LIST OF ABBREVIATIONS

Abbreviation or special term	Explanation
Acute thrombosis	AT
Body mass index	BMI
Cerebral venous sinus thrombosis	CVST
Commissioning Data Set	CDS
Computerised medical record	CMR
COVID-19 Hospitalization in England Surveillance	COVID-19 SARI-Watch/CHESS
System	
Data Access Request Service	DARS
Data and Connectivity: COVID-19 Vaccines Pharmacovigilance network	DaCVaP
Deep vein thrombosis	DVT
Direct oral anticoagulants	DOACs
General practitioners	GP
GPES data for pandemic planning and research	GDPPR
High Dependency Units	HDU
Hormone replacement therapy	HRT
Hospital Episode Statistics	HES
Index of Multiple Deprivation	IMD
Integrated research application system	IRAS
Intensive Care Units	ICU
Joint Committee on Vaccination and Immunisation	JCVI
Low weight molecular heparin	LWMH
Medicines & Healthcare products Regulatory Agency	MHRA
Middle East respiratory syndrome	MERS-CoV
Myocardial infarction	MI
National Health Service	NHS
Nested case-control study	NCCS
Office for National Statistics	ONS
Oxford Royal College of General Practitioners Clinical Informatics Digital Hub	ORCHID
Oxford-Royal College of General Practitioners	RCGP
Platelet factor 4	PF4
Principal Investigator	PI

Abbreviation or special term	Explanation
Public Health England	PHE
Pulmonary embolism	PE
Relative incidence	RI
REporting of studies Conducted using Observational Routinely-collected Data	RECORD
Research and Surveillance Centre	RSC
Second Generation Surveillance System	SGSS
Self-controlled case series	SCCS
Strengthening the Reporting of Observational Studies in Epidemiology	STROBE
Thrombocytopenia	TP
Thromboembolism	TE
Trusted research environment	TRE
United Kingdom	UK
Venous thromboembolism	VTE

### 4. ABSTRACT

Background/Rationale: A very rare syndrome of thrombosis associated with low platelets has been reported in a few cases of recent exposure to COVID-19 vaccine. No causal association with COVID-19 vaccination has yet been established. As of 15 April 2021, over 29.4 million doses of the AstraZeneca vaccine had been administered in EU/EEA countries. [1] Medicines & Healthcare products Regulatory Agency (MHRA) had requested for all cases of thrombosis or thrombocytopenia occurring within 28 days of coronavirus vaccine to be reported via the online yellow card system. [1] This thrombotic thrombocytopenia syndrome seems to be affecting patients of and and at the property of the patients of and and at the property of the patients of and and at the property of platelets following the use of the COVID-19 Vaccine AstraZeneca. The United Kingdom (UK) is uniquely placed to study this area because of its registration-based primary care system, and a unique identifier umber links primary care to secondary care data. Additionally, vaccination is well advanced maximising population wide vaccine exposure.

**Objectives:** To evaluate an association between COVID-19 vaccine exposure and thromboembolic events occurring with thrombocytopenia (thrombotic thrombocytopenia syndrome; TTS).

#### Methods:

**Study design:** Two primary study designs will be considered, a case control study and a self-controlled case series (SCCS). A cohort analysis will be considered, in addition or as an alternative to either of the primary study designs, pending feasibility assessment of the follow-up time.

**Data Source(s):** We will conduct retrospective studies using linked secondary databases in England. Data for the definitive study accessed through the NHS Digital Trusted Research Environment (TRE), providing national data coverage. Primary care data will be linked with vaccination, hospitalization, COVID-19 test results, mortality data. Initial exploratory analyses will be conducted using the

Study Population: Subjects of interest are people who

However, we will required access to data from patients, in the integrated health records of at the start of each study period. We need to make comparisons with unvaccinated, and our analysis needs information about levels of infection across the whole population.

Variables: Demographic, socioeconomic descriptors, clinical diagnosis, vaccines, potential confounders, thrombotic phenomena, COVID-19 infection, and other characteristics as applicable.

**Statistical Analysis:** Counts of cases will be reported by will start on December 02, 2020, when the COVID-19 vaccine was first approved in the UK and will end approximately by end in May or at the end of data availability.

For the case-control design, all cases of TTS will be matched with control using risk-set matching. A case or matched control will be considered exposed if a COVID-19 vaccination will be within risk interval prior to the diagnosis date of the matched case.

For the SCCS, estimates of relative incidence (RI), in all risk intervals will be reported. RI will also be reported in the Joint Committee for Vaccinations and Immunisation's (JCVI's) vaccination risk and age groups. Seasonal effects are not deemed relevant. Cumulative hazard plots for gap times will be provided, and we will investigate if the inclusion of pre-exposure risk periods affects incidence of adverse events of interest associated with vaccination using a sequence of values and exploring whether RI is sensitive to the choice of pre-exposure period.

For the retrospective cohort design, the incidence of TTS after receiving COVID-19 vaccine will be estimated and we will compare this incidence with that occurring in an unvaccinated comparator group. We will look at the concurrent unvaccinated and retrospective comparator groups.

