The Medicines and Healthcare products Regulatory Agency (MHRA) had requested for all cases of thrombosis or thrombocytopenia occurring within 28 days of coronavirus vaccine to be reported via the online yellow card system.  Up to and including 31 March 2021, the MHRA had received 79 United Kingdom (UK) reports of blood clotting cases alongside low levels of platelets following the use of the COVID-19 Vaccine AstraZeneca: 44 of the 79 cases were of cerebral venous sinus thrombosis (CVST) with thrombocytopenia 35 of the 79 cases were of thrombosis in other major veins with thrombocytopenia. These 79 cases occurred in 51 women and 28 men, aged from 18 to 79 years.  As of Apr 9, 5 cases of arterial thrombosis, 374 cases of deep vein thrombosis, 3 cases of jugular vein thrombosis, 7 cases of pelvic venous thrombosis, 1 subclavian vein thrombosis, 345 cases of thrombosis, one case of vena cava thrombosis, 21 cases of venous thrombosis and 22 cases of venous thrombosis limb, have being reported in the in the EudraVigilance database. 

Benefits are well-established while risks are very low, so it should continue to be used. In addition, recently drafted cases definitions being posed by the Brighton Collaboration currently suggest the following diagnoses are also of interest in defining probable cases: deep vein thrombosis (DVT), pulmonary embolism (PE), stroke, and myocardial infarction (MI).

The UK is one of the first countries that are introducing mass vaccination campaign for COVID-19 and has completed vaccinating the older half of the adult population starting from the oldest [10] Three age groups, by May 2021vaccien was being offered to people COVID-19 vaccines were licensed and are being used including the: Moderna, BioNTech/Pfizer, and Oxford/Astrazeneca vaccines. Vaccination with the BioNTech/Pfizer vaccine started in December 2020 and with the Oxford/AstraZeneca vaccine started in early January 2021. Also, The UK is uniquely placed to study this area because of its registrationbased primary care system (one patient registers with a single general practitioner), and a unique identifier National Health Service (NHS) number links primary care to secondary care data.

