#### 8. **OBJECTIVE**

To evaluate an association between COVID-19 vaccine exposure and the outcome of thrombosis with thrombocytopenia syndrome (TTS).

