The matched case-control study will be conducted to determine the likelihood of those presenting with thrombotic thrombocytopenia (TTS) events within a risk window of 28 days of receiving COVID 19 vaccination. Patient who fulfils the definition of thrombotic thrombocytopenia based on a distribution of TTS spontaneously reported cases for COVID-19 vaccine AstraZeneca (sensitivity windows of 42 days as risk window for many immune-mediated vaccine safety events and as per EMA recommendation. We will conduct exploratory analyses on the dataset with the definitive analysis conducted on the national data held in the NHS Digital TRE, to identify people who presented with thrombotic, and thrombocytopenia events over a period (02 December 2020 to end of data availability, estimated mid May 2021) following COVID-19 vaccination. Electronic records of cases will be checked for any previous recorded history of conditions consisting of TTS; several wash-out periods will be considered including prior 90 days or prior for 12 months prior to the date of the index episode. Those without a previous record will be deemed to have experienced an incident diagnosis of a TTS on that date. Each incident case will be matched by date of TTS event,

Diagnosis dates of the cases will be considered the index dates for the controls. Records of both cases and controls will then be checked for the 28 days (sensitivity period of 42 days) before the index date for a previous ChAdOx1 and BNT162b2 or other COVID-19 vaccination.

For the self-controlled case series (SCCS), only individuals with a TTS event recorded during the defined study time are included in the analysis. Event and exposure history will be obtained from the linked dataset; events primarily extracted from hospital data. We will control for potential delaying of vaccination by the occurrence of an event by using the pre-vaccination risk period -7 to -1 days. Furthermore, since venous thromboembolism (VTE) is a likely indication for administration of a vitamin K antagonist (warfarin) or direct oral anticoagulants (DOAC), SCCS models with both vaccination and anticoagulation as exposures are potentially subject to event-dependent exposures, including recent infection. In this case we will perform a subgroup analysis of those with historical anticoagulation (defined by a prescription for

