#### 9.6.4 Matched case-control

For matched case-control analysis, the sampled risk sets will be represented matched strata, which will be included in conditional logistic regression models to estimate odds ratios (OR) for the risk of the event in the 42-day risk period.

. Confounding may to be due to time varying confounders that will be much harder to adjust for than in our case-control study. We will also have confounding due to the differential availability of the vaccines, their storage requirements and intervals between doses (initially short and applied mainly to one brand) and then lengthened. We may be able to adjust for those that are measured and complete;

as well as recognising others may be unmeasured (such as occupation). We will stratify exposure by dose as an exploratory analysis.

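### The case-control exposure rule puts people vaccinated before the risk window into the reference with the unvaccinated, so the odds ratio contrasts recent vaccination with a shifting mix of none and earlier vaccination.

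*Protocol*

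**What the plan says.** **Exposure rule.** The Abstract (Statistical Analysis) says that any case or control alike "will be considered exposed if a COVID-19 vaccination will be within risk interval prior to the diagnosis date of the matched case". Section 9.1 makes this operational: "Records of both cases and controls will then be checked for the 28 days (sensitivity period of 42 days) before the index date". The rule is yes/no and based on a window.

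**Window length.** Section 9.1 makes 28 days the main window and 42 days the sensitivity window. Section 9.6.4 says the conditional logistic model is used "to estimate odds ratios (OR) for the risk of the event in the 42-day risk period".

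**Comparator.** The Abstract (Study Population) says "We need to make comparisons with unvaccinated". For the cohort design, Section 9.1 takes as comparators people who have had no COVID-19 vaccine so far. The objective in Section 8 asks about an association between vaccine exposure and TTS and names no comparator.

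**Role of the design.** Section 9.1 considers the case-control design the likely main analysis and the SCCS a sensitivity analysis. The cohort depends on feasibility.

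**Coverage and dosing.** Section 7 says that the UK "has completed vaccinating the older half of the adult population", beginning with the oldest. Section 9.1 puts the two doses about 90 days apart.

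**Related exclusion.** Section 9.2.1 drops people with a second dose in the follow-up window. It does not drop people whose first dose came before the window.

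**The concern.** The rule says who is exposed but does not separate two kinds of people who are not: those with no vaccine by the index date, and those vaccinated before the window opened. With doses about 90 days apart, a one-dose recipient spends weeks outside either window before the second dose. Rollout went from oldest to youngest, so the reference is mostly never vaccinated for early index dates and young strata, and increasingly past vaccinated for late index dates and old strata.

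Two things are at stake. The likely main analysis would estimate a different contrast from the cohort analysis that may supplement or replace it, so the two results could differ for reasons unrelated to bias or chance. And odds ratios by age or calendar period would rest on references of different composition, which makes them hard to compare.

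**Working it through.** The protocol gives no figure for the make-up of the reference, so there is none to reproduce. The check has three steps; the inputs marked as assumed are not in the documents.

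**1. Share of past vaccinees in the reference (q).**

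Inputs:
- Period: 2 December 2020 to mid-May 2021 (Section 9.1), taken as 15 May, T = 164 days.
- Window w: 28 or 42 days (Sections 9.1 and 9.6.4).
- Coverage V at the end of the period: assumed 30%, 50% or 70%, rising evenly.

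Formulas: recent = V × w/T; past = V − recent; q = past / (past + 1 − V).

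For V = 50%, w = 28: recent = 0.50 × 28/164 = 0.085; past = 0.415; q = 0.415 / 0.915 = 0.45.

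| V at end | q, 28-day window | q, 42-day window |
|---|---|---|
| 30% | 26% | 24% |
| 50% | 45% | 43% |
| 70% | 66% | 63% |

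Lengthening the window from 28 to 42 days changes q by only 2 to 3 percentage points, so the 42-day analysis does not remove the mixture.

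The share moves with calendar date. For V = 50% and w = 28, at the midpoint (day 82) 25% are vaccinated: recent 0.085, past 0.165, q = 0.165 / 0.915 = 18%. At day 28 it is zero.

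**2. Effect on the odds ratio.**

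Let RRw be the risk in the window and RRp the risk after it, both relative to never vaccinated. With a mixed reference, approximately:

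OR = RRw / [(1 − q) + q × RRp]

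RRw and RRp are assumed. For RRw = 3:

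| RRp | q = 0.45 | q = 0.50 |
|---|---|---|
| 0.7 | 3 / 0.865 = 3.5 | 3 / 0.85 = 3.5 |
| 1.0 | 3.0 | 3.0 |
| 1.5 | 3 / 1.225 = 2.4 | 3 / 1.25 = 2.4 |
| 2.0 | 3 / 1.45 = 2.1 | 3 / 1.5 = 2.0 |

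The direction depends wholly on RRp. A never-vaccinated reference targets RRw whatever RRp is.

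**3. Days 29-42 alone.**

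If the main window is 28 days, the share of the reference that is 29-42 days after a dose is, at V = 50%, (0.50 × 14/164) / 0.915 = 0.043 / 0.915 = 4.7%. A true odds ratio of 4 becomes 4 / (1 + 0.047 × 1) = 3.8 if risk in that band is doubled, and 4 / (1 + 0.047 × 3) = 3.5 if it stays fourfold. If the main window is 42 days, as Section 9.6.4 reads, this component disappears.

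**The case against.** Much can be said for the plan.

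- **A window-based exposure is a standard choice for a transient risk.** If risk returns to baseline after the window and past vaccinees are otherwise comparable, the odds ratio equals the recent-versus-never contrast. This stands, but the visible text does not state that assumption.
- **A reader might infer that the odds ratio fails the protocol's stated objective.** The documents do not support that. Section 8 names no comparator. The need for unvaccinated comparisons appears in the abstract's partly removed study-population text, and the not-yet-vaccinated comparator belongs to the cohort design.
- **A reader might infer a demonstrated attenuation, or a large one from days 29-42.** Neither is shown. The direction can be nil or reversed, and the 29-42 day band is about 5% of the reference under even uptake at 50% coverage. Shares of 20-30% would need rollout concentrated in particular age and date strata. The 42-day analysis also counts that band as exposed.
- **Section 9.12 already warns of attenuation from uncertain risk periods.** It does, in general terms, but it does not address who forms the reference.
- **Unexposed is never defined in the visible text, and text is missing around the matching criteria, the exposure definition and the case-control methods.** The composition of the reference is therefore an inference. It follows from a rule given in both the Abstract and Section 9.1, and no visible exclusion contradicts it.
- **Never-vaccinated older adults may be few and selected by spring 2021.** This stands as a reason not to rely on them alone.

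**Conclusion.** The point holds as a matter of what the odds ratio measures. Read as written, the likely main analysis compares recent vaccination with a mix of no vaccination and earlier vaccination. Under the even-uptake assumption, past vaccinees are about 26% to 66% of that mix by mid-May for 30% to 70% coverage, and about 45% at 50%. The share is lower earlier in the period and higher in older groups.

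This is out of line with the abstract's need for unvaccinated comparisons and with the cohort comparator. Any distortion relative to a never-vaccinated reference rests on risk after the window, which the documents do not give: for an assumed RRw of 3 and q near one half, the result runs from about 3.5 (RRp 0.7) through 3.0 (RRp 1) to about 2.0 (RRp 2). An unknown direction is itself a reason to separate the groups.

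This should be changed. The exposure rule is fixed in the protocol, so it is more than detail left to the SAP.

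**What to change.** 1. In the same conditional logistic model, code time since last dose at the index date as: never vaccinated (reference); within the risk window; days 29-42, if the main window is 28 days; more than 42 days.
2. Report recent versus never vaccinated as the main contrast, and recent versus past vaccinated alongside it. Both come from the one model.
3. Reconcile the 28-day main window in Section 9.1 with the 42-day risk period in Section 9.6.4, since this decides whether days 29-42 count as exposed.

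**Cost.** One variable is recoded from vaccination dates already linked; no new data are needed. Precision falls because the reference for the main contrast shrinks: under the even-uptake illustration with a 28-day window, at the end of the period it is 1 − 0.45 = 55% of the mixed reference at 50% coverage, and 1 − 0.66 = 34% at 70%. In the oldest strata never-vaccinated controls may be few and unlike the vaccinated, so intervals widen and selection is possible. Showing both contrasts lets the reader judge this: agreement would support a transient risk, and disagreement would point to persisting risk or to differences between the groups.

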. The rationale for matching on calendar date is to control for the temporal variation in the SARS-CoV-2 circulation (COVID-19 infection may affect risk of some AESIs) and expected changes in vaccinee characteristics over time. Propensity scores (PS) will be used to address confounding, balancing multiple covariates such as prior COVID-19 infection, comorbidities, and markers of health care utilisation between vaccinated and unvaccinated cohorts. Relative risk will be the main measure of effect, which will be estimated using incidence rate ratios (IRRs) or hazard ratios (HRs), depending on the analysis and outcome. The proposal to use concurrent, rather than historical, comparator (unvaccinated) subjects is because they are at risk for COVID-19, and COVID-19 may function as an important covariable in the analyses of several of the safety endpoints. The potential challenge with this approach is that during the pandemic, unvaccinated subjects in the comparator group may themselves become vaccinated over time. The rationale for not selecting historical pre-pandemic subjects for primary comparison pertains to concerns over non-comparability. The background rate of TTS may have changed during the pandemic because of COVID-19 or because of less intensive ascertainment due to access issues or health-seeking behaviours.

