## 9.6.3 Self-controlled case series (SCCS)

For comparative analysis using the SCCS approach, conditional Poisson regression will be used to estimate IRRs and 95% CIs. Estimates of relative incidence (RI), in all risk intervals and by age groups will be reported.

Exploratory analyses may stratify by dose, depending on available sample size. Time-invariant confounders will be inherently adjusted for using the SCCS design; however, time-varying confounders (e.g. recent prior infection) will be included as covariates in regression models.

5]

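### The abstract rules out seasonal effects for the SCCS without a reason, although 9.1 treats calendar time as a source of confounding; calendar-period terms should be added

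*Protocol*

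**What the plan says.** The Statistical Analysis part of the protocol abstract (section 4) says, in its SCCS paragraph, "Seasonal effects are not deemed relevant". No reason follows. The same paragraph promises RIs for the JCVI risk and age groups.

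Elsewhere the protocol treats calendar time as a matter to be controlled:

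- Section 9.1, on the cohort: "The rationale for matching on calendar date is to control for the temporal variation in the SARS-CoV-2 circulation", with the added remark that infection may affect the risk of some events.
- Section 9.1, on the choice of comparator: "The background rate of TTS may have changed during the pandemic because of COVID-19 or because of less intensive ascertainment due to access issues". It also names the way people seek care. This sentence explains why pre-pandemic comparators are not used: "The rationale for not selecting historical pre-pandemic subjects for primary comparison pertains to concerns over non-comparability".
- Section 9.1, on the case-control study: cases are matched by date of the TTS event. No reason is stated there.

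For the SCCS model, section 9.6.3 says that "conditional Poisson regression will be used to estimate IRRs and 95% CIs", notes that the design itself adjusts for time-invariant confounders, and adds that "time-varying confounders (e.g. recent prior infection) will be included as covariates in regression models". Section 9.1 plans a prior-infection subgroup. Section 9.8 plans a sensitivity analysis censored before the first media reports, dated 7 March 2021. No visible section puts a calendar-time term in the SCCS model.

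**The concern.** An SCCS compares risk time with control time within the same person, so anything that changes with the calendar is not removed by the design. It matters when exposure is also tied to the calendar, and here it is. Section 7 has AstraZeneca vaccination starting in early January 2021, and the older half of adults vaccinated from the oldest down. The SCCS window in 9.1 runs from 26 October 2020 to about mid May 2021. Where a person's risk period falls relative to any winter wave, or to any rise in diagnostic awareness in March, therefore depends on when, and so roughly at what age, that person was vaccinated.

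If the background rate moves, the fitted RI mixes the vaccine effect with a period effect. The direction can differ between early and late vaccinees, so RIs by age group, which are a stated output, could differ for reasons unrelated to the vaccine. This is more than a detail left to the SAP: the abstract takes a positive decision against handling it.

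**Working it through.** The protocol gives no figure to reproduce on this point. The check asks how far the fitted RI moves from 1 when the true RI is 1 and the background rate varies.

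**Inputs from the protocol.** Window 26 October 2020 to 15 May 2021 (mid May, section 9.1): 6+30+31+31+28+31+30+15 = 202 days. Risk days 0-28 (9.1 splits them into 0-2 and 3-28; merged here): 29 days. Pre-vaccination days -7 to -1: 7 days, set apart. Control days: 202 - 29 - 7 = 166. Conditional Poisson model (9.6.3). Ascertainment change placed at 7 March 2021, the date in 9.8.

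**Assumptions, not in the protocol.** Background multiplied by f = 1.5 or 2, either in a winter wave from mid-December to mid-February (15 December to 13 February, 17+31+13 = 61 days) or from 7 March on (25+30+15 = 70 days). Vaccination dates uniform over the named months. No infection covariate.

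**Formula.** For people vaccinated on one date, the fitted RI without calendar terms tends to

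RI = (mean background rate over risk days) / (mean background rate over control days).

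*Vaccinated 1 April.* Risk days are 1-29 April; days -7 to -1 are 25-31 March.

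- Ascertainment: all 29 risk days are raised; raised control days 70 - 29 - 7 = 34, others 132. RI = 166f/(132 + 34f), so 249/183 = 1.36 for f = 1.5 and 332/200 = 1.66 for f = 2.
- Wave: no risk day is raised; 61 control days are, 105 are not. RI = 166/(105 + 61f), so 166/196.5 = 0.84 and 166/227 = 0.73.

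*Vaccinated 11 January.* Risk days run to 8 February, all inside the wave.

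- Wave: raised control days 61 - 29 - 7 = 25, others 141. RI = 166f/(141 + 25f), so 249/178.5 = 1.39 and 332/191 = 1.74.
- Ascertainment: no risk day is raised; 70 control days are, 96 are not. RI = 166/(96 + 70f), so 166/201 = 0.83 and 166/236 = 0.70.

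Under both scenarios the direction reverses between the early and the late vaccinee.

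**Spread-out vaccination dates.** Solving the expected score equation, the sum over dates of [A - (A + C)·RI·29/(RI·29 + 166)] = 0, with A and C the background summed over risk and control days (day counts reduced where a window runs past 15 May), gives for f = 1.5 / 2:

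| Vaccinated | Winter wave | Ascertainment from 7 March |
|---|---|---|
| January-April | 0.97 / 0.95 | 1.12 / 1.21 |
| January-February | 1.10 / 1.19 | 0.90 / 0.83 |
| February-April | 0.87 / 0.77 | not tabulated |
| March-April | not tabulated | 1.35 / 1.63 |

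With a flat background the RI is 1.00. Using a smooth wave peaking on 10 January and the same 7 March step, a model with 14-day calendar bands brought the RI back to 0.98-1.01 in every scenario tried.

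**What the planned safeguards do.** Ending observation at 7 March returns the January-February ascertainment case to 1.00, but people vaccinated later drop out. It does not touch the winter wave: those vaccinated from February still show about 0.86 / 0.77. The infection covariate can absorb the part of a wave that passes through recorded infection, so the wave figures are upper bounds to the extent that it succeeds.

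**The case against.** The strongest reply is that the plan already deals with the main pathway. The one thing 9.1 presents as varying over calendar time is SARS-CoV-2 circulation, and 9.6.3 puts recent infection in the SCCS model, in an open list of time-varying confounders. The March awareness shift has its own sensitivity analysis in 9.8. With vaccination spread over January-April the illustrated bias is small to moderate, and every multiplier is assumed. Calendar terms cost precision with a very rare outcome, most of all in the age groups they are meant to protect. Section 9.1 also expects the case-control study, matched by event date, to be the main analysis.

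Much of this stands. It limits the size of the problem and rules out three stronger readings that a reader might infer:

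- *That 9.1 says the background rate and ascertainment did change over the study period.* It says only that "The background rate of TTS may have changed during the pandemic", in arguing against pre-pandemic comparators.
- *That the RI is shown to be confounded.* What the documents support is a risk of residual confounding.
- *That the main result is undermined.* The event-date-matched case-control study does not depend on this sentence.

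The reply does not rescue the sentence itself. Unrecorded infection, access to care and diagnostic awareness are not captured by an infection covariate. The 7 March censoring is a secondary analysis that says nothing about later vaccinees. A sensitivity analysis left open to calendar-time confounding is also a weak check on a main analysis matched by event date.

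**Conclusion.** The point holds as an unexplained statement that conflicts with the protocol's own reasoning and leaves a risk of residual calendar-time confounding in the SCCS. For the overall RI under January-April vaccination, the assumed 1.5-fold / 2-fold shifts move a true RI of 1 by about 3-5% downward (wave) or 12-21% upward (ascertainment). For groups vaccinated in a narrower, later window the shift is about 13-23% downward (February-April, wave) or 35-63% upward (March-April, ascertainment). These sizes rest on assumed multipliers, uniform vaccination dates and no infection covariate; the protocol supplies none of them, and they do not show that a bias exists.

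The consequence is greatest for the age-group RIs. It is bounded by the role of the SCCS, which 9.1 describes as a sensitivity analysis for non-fatal cases, although the abstract calls it one of two primary designs. The change should be made, but the study does not stand or fall by it.

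**What to change.** Delete the sentence on seasonal effects from the abstract and reconcile the SCCS description with 9.1 and 9.6.3. In 9.6.3:

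- Add calendar-period terms to the conditional Poisson model, for example monthly. Shorter bands follow a sudden change more closely but use more parameters.
- Share the calendar effect across age groups instead of estimating it within each.
- State that unvaccinated TTS cases are retained, since they inform the calendar effect. Section 9.1 does not exclude them but does not say so.
- Report the fit without calendar terms as a sensitivity analysis.

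No new data are needed, and section 9.5 already names the SCCS library for R.

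The cost is precision. With vaccination spread over January-April, the standard error of the log RI rises by about 3-6%. For an age group vaccinated within about four weeks (an assumption) and analysed on its own, it rises by about 40-70% without unvaccinated cases and 15-21% if half the cases are unvaccinated. That is why the calendar effect should be shared and those cases kept. If few unvaccinated cases are available, the wider age-group intervals should be accepted and stated.
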